The endpoint for Aim 1 for the intervention arm is the successful completion of the follow-up period, including food and nutrition security status, total fruits and vegetables selected per visit, total energy intake, intake of key food groups, and time to obtain food from food pantry per visit.

The endpoint for Aim 2 is the completion of data analysis.

Study Population

The study population for Aim 1 is a sample of low-income adults aged ≥ 18 years..

Accrual Ceiling

We require a total sample size of 193 participants per condition for Aim 1 (total n=386).

Aim 2 will not involve participant enrollment.

Phase

Not applicable.

Description of Sites/Facilities Enrolling Participants

We propose to recruit participants from food pantry clients at food pantry sites within the Met Council Kosher Food Pantry Network, a network that contains 65 pantry partners and over 200 community partners in NYC. Met Council procures and distributes kosher food to their network of kosher food pantries and provides ongoing support with reporting, pantry set up and maintenance, advocacy, and programming. The Network primarily serves immigrants, seniors living on fixed incomes, the un- and underemployed and anyone else in need in immigrant-dense neighborhoods.

Study Duration

The study will last 18 months, but data collection will specifically occur in 2 time periods, including months 4-6 and 10-12 in Year 1 of the study.

Participant Duration

The total participant duration will be approximately 30-50 minutes to complete the survey and record food selections for both data collection periods.

Schedule of Activities (SoA)

During the baseline data collection period, all participants will complete a survey about their food and nutrition security, diet behaviors, and frequency of food pantry visits. To finish, the Research Assistant will record their food selections from the current food pantry visit.

During the follow-up data collection period, all participants will complete a survey about their food and nutrition security, diet behaviors, and frequency of food pantry visits. Participants in the control arm will record their food selections from their most recent food pantry visit and send them to the study team.

End of Study Definition

The end of the study is when we have disseminated our results.

1 – Statement of Compliance

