4.1 Overall Design

This research study includes two aims, though only Aim 1 involves human subjects. The duration of the study is 18 months.

In Aim 1, study team members will recruit low-income adults aged ≥ 18 years. Participants will be recruited from a food pantry that is not scheduled to transition to online ordering (control) and a food pantry that is scheduled to transition to online ordering after the baseline data collection period (intervention). Participants in both arms will complete an in-person survey. Potential participants who are not able to take the survey in-person, will be offered the option to take the survey online. To assess potential changes in fruit and vegetable intake, we will administer the Behavioral Risk Factor Surveillance System (BRFSS) 6-item brief dietary assessment tool (questions 9-14 in the survey attached in Research Navigator). A Research Assistant will record the food items they received in the relevant visit to the pantry. After the transition to online ordering at the intervention food pantry, participants will again complete the survey over the phone. The survey will be administered by a member of the study team using the Follow-Up Survey Guide. Participants in the control arm will record their food selections and send them to the study team during the phone call. Food selections for participants in the intervention arm will be accessible through the online ordering platform. The study team will then analyze the baseline and follow-up data for differences in outcomes between study conditions.

In Aim 2, we will test for potential interaction effects at the individual-level by adding an interaction term for age group (18-61 vs. ≥ 62 years).

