5.5 Strategies for Recruitment and Retention

For Aim 1, we will choose the food pantry recruiting sites with help from Met Council Kosher Food Pantry Network. We will aim to select a control site that is similar to the intervention site based on food pantry characteristics (e.g., number of food pantry clients per week, primary language(s) spoken) and community-level characteristics (e.g., neighborhood poverty level).

IRB-approved NYULH study personnel will recruit participants in person at two Met Council food pantries and will obtain permission from the food pantries prior to in-person recruitment at their

facilities. We will have support from food pantry staff members in introducing the NYULH study to potential participants. The study personnel will be on-site at the food pantry to introduce the study to food pantry clients and answer questions. Food pantry staff will also be available to direct food pantry clients to the study personnel. The study team will provide the food pantry with a recruitment flyer to post and/or pass out informing clients of the study and directing them to scan a QR code for the consent form with more information about the study and access to the study team's contact information. After scanning the QR code, clients will first see a short paragraph ("Pre-Consent QR Code Copy") listing the eligibility requirements and explaining what the consent is, in addition to a note that they do not need to sign the form at that moment. After the short paragraph, they will be able to scroll down to view the consent.

We will collect names, phone numbers, email addresses, and mailing addresses from participants in a secure REDCap form to facilitate the follow-up data collection, which will be conducted virtually, and to distribute gift cards.

Screen failures include those who do not meet all of our inclusion criteria. Potential participants will be asked to answer one pre-screening question about their age to determine their eligibility. If they do not meet our inclusion criteria, these participants will be told by the Research Assistant, "Thank you for your time, but unfortunately, you are not eligible for this study." We will immediately discard information from screen failures and from individuals that do not provide consent to take part in this study. Re-screening is not applicable.

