8.4 Statistical Analyses

We will perform a linear regression to assess balance of demographic characteristics between conditions; because of the natural experiment design, these characteristics should be balanced. To assess differences in outcomes between study conditions, we will regress the outcome variable on indicator variables for the experimental conditions, with the control condition as the reference group; if necessary, we will also adjust for any respondent characteristics that may be unbalanced by condition. The design and methods proposed will achieve robust and unbiased results because random assignment to an intervention group or control group in the context of a natural experiment minimizes bias.

We will also test for potential interaction effects at the individual-level by adding an interaction term for age group (18-61 vs. ≥ 62 years). In the food pantry network, an average of 25% of clients served are above 61 years of age, so we will have adequate variation to assess potential interactions by age group. For assessing differences in the frequency of food pantry visits per month at the food pantry-level, we will also add an interaction term for age group, which the

food pantry network measures as child (<18 years), adult (18-61 years), and older adult (≥ 62 years).

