8.4.3 Analysis of the Secondary Endpoint(s)

The secondary outcomes for Aim 1 include changes in: 1) total cup-equivalents of fruits and vegetables selected per visit; 2) intake of fruits and vegetables; 3) time to obtain food from food pantry per visit (minutes); and 4) individual-level frequency of food pantry visits per month (n). To capture a potential increase in *new* clients visiting the food pantry due to the transition to online ordering, we will also measure changes in the frequency of food pantry visits per month at the food pantry-level (n).

The primary outcome for Aim 2 is the same as Aim 1 and measured using the same specifications, including number of fruits and vegetables selected per visit; total energy intake; intake of key food groups; time to obtain food from food pantry per visit; and individual-level and food pantry-level frequency of food pantry visits per month. For assessing differences in the frequency of food pantry visits per month at the food pantry-level, we will add an interaction term for age group, which the food pantry network measures as child (<18 years), adult (18-61 years), and older adult (≥ 62 years).

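### The pantry-level visit outcome rests on one pantry per condition, so the stated regression gives either no standard error or one that leaves out pantry-level change; report it descriptively unless further pantries can be added

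*Combined protocol and SAP*

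**What the plan says.** **Sites.** Section 4.1 draws participants from "a food pantry that is not scheduled to transition to online ordering (control) and a food pantry that is scheduled to transition" after baseline. Section 5.5 says that study staff "will recruit participants in person at two Met Council food pantries". Both give one pantry per condition.

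**Outcome.** After the four numbered secondary outcomes, section 8.4.3 adds a pantry-level one, meant to capture new clients who come because of online ordering: "we will also measure changes in the frequency of food pantry visits per month at the food pantry-level (n". Sections 8.4, 8.4.3 and 8.4.8 add an age-group interaction to it (in the words of 8.4, "For assessing differences in the frequency of food pantry visits per month at the food pantry-level"), using a grouping "which the food pantry network measures as child (<18 years), adult (18-61 years), and older adult (≥ 62 years".

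**Model.** The only model stated (8.4, 8.4.2, 8.4.8) regresses the outcome on condition indicators with control as reference, adjusting for unbalanced respondent characteristics if needed. The plan does not say whether a row is a month, a period or an age band. It gives no pantry term and no variance method, and does not limit this outcome to description.

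**Months.** Section 6.1 sets baseline at t-4 to t-2 and follow-up at t+2 to t+4, and leaves out t-1 and t+1.

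**Network.** The Synopsis (Description of Sites/Facilities Enrolling Participants) describes "a network that contains 65 pantry partners and over 200 community partners in NYC".

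**The concern.** Visit counts at a pantry move for many reasons: opening hours, supply, a nearby pantry closing, holidays. With one pantry per condition, any such change at either pantry has the same form in the data as an effect of online ordering. More months or age bands add rows but no pantries.

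Sections 4.2, 8.4 and 8.4.8 invoke random assignment. Section 5.4 says that the pantry itself brings about the change, and 5.5 says that the control site is selected for similarity. Randomisation therefore cannot supply the missing error term.

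The outcome has a causal purpose in 8.4.3, and section 2.3.2 expects pantries to consult the results when deciding whether to move online. A p-value that reflects only monthly noise could be read as evidence that online ordering brings in new clients.

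**Working it through.** The plan gives no sample size, power or precision for this outcome, so there is no figure of its own to reproduce. The 155 per condition in 8.2 concerns the individual food security score and does not bear on it.

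**Inputs from the plan.** 2 pantries (4.1, 5.5); 3 baseline and 3 follow-up months (6.1); 3 age bands (8.4, 8.4.3); at most 65 − 1 = 64 other pantry partners (Synopsis).

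**Assumed.** Month-to-month SD 1; a pantry-by-period shock with SD τ between 0 and 2; no true effect. Because 8.4.3 speaks of changes, the contrast is taken as the intervention pantry's change minus the control pantry's change.

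**Step 1: degrees of freedom.**
- One change per pantry: 2 rows − 2 parameters = 0.
- One change per pantry and age band: 6 rows − 6 parameters = 0.
- Monthly rows: 2 × 6 = 12 rows − 4 parameters = 8, all of them within pantry and period.

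The first two readings give no standard error. The third gives one with no between-pantry component.

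**Step 2: size of the error with monthly rows.** The contrast uses four cell means, each with variance τ² + 1/3.
- True variance: 4(τ² + 1/3).
- Variance that the regression estimates: 4 × 1/3.
- Ratio: 1 + 3τ².

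The rejection rate is therefore P(|t₈| > 2.306 / √(1 + 3τ²)).

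| τ | √(1 + 3τ²) | Effective cut-off | Rejection rate |
|---|---|---|---|
| 0 | 1.000 | 2.306 | 5.0% |
| 0.25 | 1.090 | 2.116 | 6.7% |
| 0.5 | 1.323 | 1.743 | 12.0% |
| 1 | 2.000 | 1.153 | 28.2% |
| 2 | 3.606 | 0.640 | 54.0% |

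Simulation agrees: 4.9%, 6.5%, 12.1%, 28.3% and 54.2% (20,000 runs each).

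**Step 3: age interaction.** Take older adults against adults, with 2 × 2 × 3 × 3 = 36 monthly rows and 12 cell means, so 24 df. A pantry shock shared by all ages cancels in the contrast, and simulated rejection is 5% at τ = 0, 1 and 2. If the shocks are age-specific, the ratio 1 + 3τ² returns and the rate is P(|t₂₄| > 2.064 / √(1 + 3τ²)): 13%, 31% and 57% at τ = 0.5, 1 and 2.

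**Step 4: what further control pantries would buy.** With J controls, the smallest one-sided rank p-value is 1/(J + 1): 0.50 for J = 1, 0.091 for J = 10, 0.050 for J = 19, and 1/65 = 0.015 for J = 64. The standard error of the contrast falls by √((1 + 1/J)/2), which is 0.73 at J = 19.

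The unit of analysis matters as much as the number of pantries. With 19 or 63 controls, monthly-row regression still rejects 32% to 33% at τ = 1. An analysis of one change per pantry stays between 4.8% and 5.2% at every τ tested.

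**Step 5: limit of that remedy.** Ranks assume that the treated pantry's changes are about as variable as the controls'. If their SD is 1.5 or 2 times as large (assumed, 64 controls), a nominal 5% rank test rejects 13% or 19% one-sided, and 18% or 31% two-sided.

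**The case against.** - **The analysis is partly the reader's construction.** The row unit is not stated, so treating months as replicates is one reading among several. This is fair, but Step 1 shows that the other readings give no standard error at all, so none yields a usable test.
- **The number of pantries feeding this outcome is not stated in so many words.** The count of two in 5.5 concerns in-person recruitment. This stands as a caveat. However, two is the natural reading, and no section names others.
- **A reader might infer that the standard errors are certainly too small and a false claim likely.** The documents do not support that. The test is at its nominal level if τ = 0, only the largest ratio tried exceeds 50%, and no pantry-level variance is given.
- **A reader might infer that the age interaction is equally affected.** Step 3 shows that this needs shocks that differ by age group.
- **A reader might infer that the network already holds monthly counts for all 65 partners.** The age-band wording, which includes children who cannot enrol, points to network records. It does not show monthly counts at every partner, and the number staying off online ordering is not given. The quoted 25% is a share of clients, not a visit count.
- **The stakes are low.** The outcome follows the numbered secondary ones and is absent from the hypotheses in 8.1 and the endpoints in 3.2. That limits the point's weight. Whether the two-site design also affects the individual-level outcomes is a separate question.

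**Conclusion.** The point holds for the pantry-level visit outcome. With one pantry per condition, the stated regression cannot separate online ordering from anything else that changed at either pantry. A valid p-value or interval requires that neither pantry has a period shock of its own, and two pantries cannot test that. Under the assumed ratios the false-positive rate runs from about 5% (no shock) to 54% (shock SD twice the monthly SD). These figures illustrate sensitivity and do not estimate the rate in this study. The age interaction is at risk only under age-specific shocks. The change should be made, but it concerns an additional outcome and not the primary one.

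**What to change.** **Default, in 8.4, 8.4.3 and 8.4.8.** State that pantry-level visits per month and their age split will be reported descriptively for the two pantries, without p-values or confidence intervals. Add that a difference will not be attributed to online ordering on this basis alone. The cost is wording only.

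**If the network can supply monthly counts for pantries that do not move to online ordering:**
- Compare the intervention pantry's change with the distribution of changes at those pantries, one change per pantry, by placebo ranks or an equivalent pantry-level analysis.
- Use t-4 to t-2 against t+2 to t+4, and leave out t-1 to t+1, in line with 6.1.
- Put changes on a relative or standardised scale, preferably among pantries similar in client volume and the other characteristics listed in 5.5.
- Exclude any pantry that also transitions.
- State the number of controls J and the smallest attainable one-sided p-value, 1/(J + 1). Nineteen controls are needed for 0.05, and 1/65 is a best case.

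This costs one data request and a short additional analysis. Reporting quality may vary between pantries, and with a single treated pantry the inference still assumes that its shocks resemble those of the controls.

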8.4.1 General Approach

For Aim 1, we will examine differences in outcomes between study conditions, including food and nutrition security, intake of key foods, and frequency of food pantry visits.

For Aim 2, we will examine differences in outcomes between adult (18-61 years) and older adult (≥ 62 years) participants.

8.4.2 Analysis of the Primary Efficacy Endpoint(s)

The primary outcome for Aim 1 is food security status. We will use the United States Department of Agriculture (USDA) six-item food security survey module to assess food security status, where the range of points is zero to six points, and higher points corresponds to lower food security.⁴¹ Food security status will be categorized according to USDA guidelines, including very low (5-6); low (2-4); and high or marginal (0-1) food security. We will perform a linear regression to assess balance of demographic characteristics between conditions; because of the natural experiment design, these characteristics should be balanced. To assess differences in outcomes between study conditions, we will regress the outcome variable on indicator variables for the experimental conditions, with the control condition as the reference group; if necessary, we will also adjust for any respondent characteristics that may be unbalanced by condition.

The primary outcome for Aim 2 is the same as Aim 1 and measured using the same specifications. We will test for potential interaction effects at the individual-level by adding an interaction term for age group (18-61 vs. ≥ 62 years). In the food pantry network, an average of 25% of clients served are above 61 years of age, so we will have adequate variation to assess potential interactions by age group.

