4.2 Scientific Rationale for Study Design

The design and methods proposed will achieve robust and unbiased results because random assignment to an intervention group or control group in the context of a natural experiment minimizes bias.

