5.4 Lifestyle Considerations

Participants in the intervention arm will have to transition with their food pantry to online ordering after the baseline data collection period regardless of their participation in this research study. The change will be brought on “naturally” by the food pantry (not the NYULH researchers or specifically as part of this research study). There will be no other restrictions during any other parts of the study pertaining to lifestyle and/or diet.

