8.4.8 Exploratory Analyses

For Aim 1, we will examine differences in outcomes between study conditions, including food and nutrition security, intake of fruits and vegetables, and frequency of food pantry visits. We will perform a linear regression to assess balance of demographic characteristics between conditions; because of the natural experiment design, these characteristics should be balanced. To assess differences in outcomes between study conditions, we will regress the outcome variable on indicator variables for the experimental conditions, with the control condition as the reference group; if necessary, we will also adjust for any respondent characteristics that may be unbalanced by condition. The design and methods proposed will achieve robust and unbiased results because random assignment to an intervention group or control group in the context of a natural experiment minimizes bias.

For Aim 2, we will examine differences in outcomes between adult (18-61 years) and older adult (≥ 62 years) participants. We will test for potential interaction effects at the individual-level by adding an interaction term for age group (18-61 vs. ≥ 62 years). In the food pantry network, an average of 25% of clients served are above 61 years of age, so we will have adequate variation to assess potential interactions by age group. For assessing differences in the frequency of food pantry visits per month at the food pantry-level, we will also add an interaction term for age group, which the food pantry network measures as child (<18 years), adult (18-61 years), and older adult (≥ 62 years).

9 – Ethical Considerations

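### The primary model does not say whether it analyses the follow-up score or the change; run on follow-up scores, it would report any persisting, unadjusted gap between two non-randomised pantries as an effect of online ordering

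*Combined protocol and SAP*

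**What the plan says.** Section 8.4.2 names food security status as the primary outcome, scored 0 to 6 with higher scores worse. It gives no time point for the analysis. The model is: "we will regress the outcome variable on indicator variables for the experimental conditions, with the control condition as the reference group". Sections 8.4 and 8.4.8 give the same model.

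Adjustment is conditional: "if necessary, we will also adjust for any respondent characteristics that may be unbalanced by condition". The accompanying check is limited: "We will perform a linear regression to assess balance of demographic characteristics between conditions". Baseline food security is named in neither, and the plan expects no problem: "because of the natural experiment design, these characteristics should be balanced".

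Section 4.2 gives the justification: "The design and methods proposed will achieve robust and unbiased results because random assignment to an intervention group or control group". Sections 8.4 and 8.4.8 repeat it, saying that "random assignment to an intervention group or control group in the context of a natural experiment minimizes bias".

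The design sections describe something else. Section 4.1 recruits from one pantry due to move to online ordering and one that is not. Section 5.4 states: "Participants in the intervention arm will have to transition with their food pantry to online ordering after the baseline data collection period". It adds that the pantry, not the researchers, brings the change about. Section 5.5 says the control site will be chosen to resemble the intervention site.

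**The concern.** Under randomisation, a follow-up comparison, a change score and a baseline-adjusted model would all estimate the same effect and differ mainly in precision. With one self-scheduled pantry and one chosen control they estimate different things, so leaving the outcome variable undefined leaves the primary estimand open.

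An analyst could follow 8.4.2 to the letter, regress follow-up scores on condition, and be compliant. The coefficient would then be the effect plus whatever part of an earlier difference between the two clienteles persists to follow-up and is not removed by adjustment. That part could create an apparent benefit or hide a real one. Choosing a similar control site may shrink the difference but does not ensure that there is none. Food security is surveyed at both waves, so a stable gap could be removed with data already planned, but the primary model does not commit to this.

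**Working it through.** **Inputs from section 8.2:** SD 1.5, difference 0.5, 155 evaluable per arm, 90% power. Alpha and sidedness are not stated.

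**Assumed, not in the documents:** alpha 5%, the size of the pantry gap, the within-person correlation rho between waves, and equal SDs at both waves.

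**1. The plan's own figure.** For a two-group comparison at one time point, n = 2 × 1.5² × (z_alpha + z_beta)² / 0.5².
- One-sided 5%: 18 × (1.6449 + 1.2816)² = 154.2, so 155. This matches.
- Two-sided 5%: 18 × (1.9600 + 1.2816)² = 189.1, so 190. This does not match; 155 per arm gives 84% power.

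The calculation has no correlation term. It also fits a change score if 1.5 is the SD of change, which is the case rho = 0.5 if 1.5 is the cross-sectional SD. It therefore does not reveal which model is meant.

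**2. Model run on follow-up scores.** SE = 1.5 × √(2/155) = 0.170. With a persisting, unadjusted gap g and no true effect, the expected estimate is g, and two-sided rejection is P(|N(g/SE, 1)| > 1.96). With a true 0.5-point improvement and the intervention pantry starting worse by g, the net difference is 0.5 − g.

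| Assumed gap g | g/SE | False rejection, no effect | Two-sided power, gap opposing a 0.5 effect |
|---|---|---|---|
| 0 | 0 | 5% | 84% |
| 0.10 | 0.59 | 9% | 65% |
| 0.20 | 1.17 | 22% | 42% |
| 0.25 | 1.47 | 31% | 31% |

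**3. The candidate models compared.** Simulation with a stable gap of 0.25, no effect, 155 per arm, 20,000 runs and two-sided 5% tests. At every rho the follow-up-only model averaged 0.25 and rejected 31% of the time; the change score averaged 0.00 and rejected 5%. Baseline-adjusted ANCOVA should leave (1 − rho) × 0.25, that is 0.175, 0.125 and 0.075. The simulation agrees:

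| rho | ANCOVA mean | ANCOVA rejection |
|---|---|---|
| 0.3 | 0.174 | 19% |
| 0.5 | 0.125 | 13% |
| 0.7 | 0.076 | 10% |

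**4. Limit of the change score.** If the pantries drift apart by 0.20 points for reasons other than online ordering, it rejects 17%, 22% and 33% of the time at rho 0.3, 0.5 and 0.7.

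**5. Power of the change contrast for 0.5 points.** SE = 0.170 × √(2(1 − rho)).

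| rho | SE | Power, one-sided | Power, two-sided |
|---|---|---|---|
| 0.3 | 0.202 | 80% | 70% |
| 0.5 | 0.170 | 90% | 84% |
| 0.7 | 0.132 | 98% | 97% |

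If the waves cannot be linked and are treated as independent samples of 155 per arm, SE = 0.170 × √2 = 0.241 and two-sided power is about 55%.

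**The case against.** The strongest reply is that the intended analysis is evidently before/after. The hypothesis in 8.1 expects improvement in one arm and not in the other; 4.1 says both waves will be analysed; 8.4.3 frames the secondary outcomes as changes; and the 0.5 in 8.2 comes from a fall from 2.8 to 2.3 in an earlier study. If the outcome variable is the change, the regression in 8.4.2 is already a change-score model. This largely stands. A reader might infer that the plan prescribes a follow-up-only analysis, and the documents do not support that. Section 3.2 ties the endpoint to follow-up data collection, but it describes a milestone, and the sample size fits either reading. What remains is that the primary model nowhere states the intent, and the intent would not choose between a change score and ANCOVA, which differ here by about (1 − rho) of a stable gap.

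The adjustment clause refers to respondent characteristics, which could be stretched to include baseline food security. Nothing commits to that, and the balance check is demographic.

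A reader might also infer that the Aim 2 interaction carries the same bias. It does not follow: a gap equal in both age groups cancels from the condition-by-age term. Bias there needs a gap that differs by age, and the documents give no evidence of one. Aim 2 shares only the undefined outcome.

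Finally, linkage is not assured. Section 9.6 describes IDs that join survey, dietary and food-selection data but does not say that they join baseline to follow-up, while 2.3.1 and 9.4 keep contact details separate from survey responses. This stands and belongs in the fix.

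**Conclusion.** The concern holds as an unspecified primary model resting on a randomisation claim that the protocol's own design sections contradict. It needs correcting before analysis because it affects the sole primary outcome and the readings open to the analyst give different answers.

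The 9%, 22% and 31% false-rejection rates illustrate sensitivity; they do not predict error. They apply only if follow-up scores are analysed, and only to the part of the gap that persists and escapes adjustment. The gap sizes, the 5% alpha and rho are assumptions. No model separates online ordering from other pantry-specific changes over time when there is one pantry per arm; a change contrast removes a stable gap and nothing more.

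**What to change.** - In 8.4, 8.4.2 and 8.4.8, define the primary contrast as the between-condition difference in change of the 0–6 score from baseline to follow-up. Name the estimator in advance: a change score or a condition-by-period term.
- Report baseline-adjusted ANCOVA as a sensitivity analysis, noting that it leaves about (1 − rho) of a stable gap.
- Use the same outcome for the Aim 2 interaction.
- State that the study ID links each participant's baseline and follow-up surveys, and reconcile this with 2.3.1, 9.4 and 9.6.
- Delete the random-assignment claim in 4.2, 8.4 and 8.4.8. State the parallel-trends assumption instead, and say that one pantry per arm cannot verify it.
- Restate the power in 8.2 with its sidedness and assumed correlation. The 90% at 155 per arm holds only for a one-sided 5% test (84% two-sided) of a single-time comparison, or of a change score at rho 0.5.

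**Cost.** No new data items are needed. Precision is lost if rho is below 0.5: at rho 0.3, power for 0.5 points is about 80% one-sided or 70% two-sided, and without linkage about 55% two-sided. Holding 90% at rho 0.3 would take 154.2 × 1.4, or 216 per arm, one-sided (189.1 × 1.4, or 265, two-sided). That is a separate decision for the sponsor: this fix requires the stated power to be corrected, not more enrolment.
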